3.3.3 Exclusion criteria

- Patients with previous exposure to Pradaxa
- Clinically significant bleeding
- **Increased risk of bleeding due to following diseases;**
Recent gastrointestinal ulceration
Recent intracranial or intracerebral bleeding history
Intraspinal or intracerebral vascular abnormalities
Recent brain, spinal or ophthalmic surgery

Proprietary confidential information. © 2014 Boehringer Ingelheim International GmbH or one or more of its affiliated companies.

Recent brain or spinal injury

Known or suspected oesophageal varices

Arteriovenous malformations

Vascular aneurysms

Presence of malignant neoplasms at high risk of bleeding

- Concomitant treatment with any other anticoagulants e.g. unfractionated heparin (UFH), low molecular weight heparins (enoxaparin, dalteparin etc), heparin derivatives (fondaparinux etc), oral anticoagulants (warfarin, rivaroxaban, apixaban etc) except under the circumstances of switching therapy to or from Pradaxa or when UFH is given at doses necessary to maintain an open central venous or arterial catheter
- Severe renal impairment ($\text{CrCl} < 30\text{mL/min}$)
- Concomitant treatment with oral ketoconazole **or dronedarone**
- Patients hypersensitive to dabigatran or dabigatran etexilate or to any ingredient in the formulation
- Prosthetic heart valve replacement
- No creatine clearance collected within at least one year prior to enrollment
- Current participation in other clinical trials

3.3.4 Removal of patients from therapy or assessments

3.3.4.1 Removal of individual patients (therapy or assessments)

This section is not applicable.

3.3.4.2 Discontinuation of the study by the sponsor

Boehringer Ingelheim Korea reserves the right to discontinue the study overall or at a particular study site at any time for the following reasons:

1. Emergence of any efficacy/safety information that could significantly affect continuation of the study
2. Violation of applicable local regulations, the NIS protocol, or the contract by a study site or participating physician, disturbing the appropriate conduct of the study.

Proprietary confidential information. © 2014 Boehringer Ingelheim International GmbH or one or more of its affiliated companies.

4. TREATMENTS

4.1 PRESCRIBED TREATMENTS TO BE OBSERVED

4.1.1 Identity of the product(s)

Pradaxa will be prescribed according to the local label and at the discretion of the treating physician. Since this is a non-interventional study, the drug will not be supplied by the sponsor. Furthermore, the sponsor will not cover the expenses related to other medications taken by the patient, interventions, procedures, or diagnostic tests.

4.1.2 Method of assigning patients to treatment groups

The choice of treatment is fully at the discretion of the physician and the patient. There is no treatment assignment by a third party.

4.1.3 Selection of doses in the study

The choice of dabigatran dose, from those two options described below, should be determined according to the local label (attachment 4) and at the discretion of the treating physician. Physician should carefully review the special precautions for use in patients with risk of bleeding (Attachment 5) before determining the dose of Pradaxa.

- Dabigatran etexilate mesilate 110 mg b.i.d. (one capsule twice daily)
- Dabigatran etexilate mesilate 150 mg b.i.d. (one capsule twice daily)

4.1.4 Drug assignment and administration of doses for each patient

This section is not applicable.

4.2 CONCOMITANT THERAPY, RESTRICTIONS, AND RESCUE TREATMENT

The protocol will allow additional drugs considered necessary for the patient's welfare to be prescribed at the discretion of the treating physician. It is required, however, to record the details of all concomitant medication administered to the patient during the course of treatment in eCRF. This includes concomitant therapies started one month prior to Pradaxa initiation until the patient completes the final follow-up visit.

4.2.1 Rescue medication, emergency procedures, and additional treatment(s)

Please refer to the current local label (Attachment 4).

Proprietary confidential information. © 2014 Boehringer Ingelheim International GmbH or one or more of its affiliated companies.

4.2.2 Restrictions

4.2.2.1 Restrictions regarding concomitant treatment

Please refer to the current local label (Attachment 4).

4.2.2.2 Restrictions on diet and life style

Please refer to the current local label (Attachment 4).

4.3 TREATMENT COMPLIANCE

During the follow-up visits, treatment compliance will be evaluated by treating physician. To minimize the recall bias, the physician could ask associating questions with specified time intervals (e.g. how often did you take Pradaxa *during the last 5 days*) to patients. An explanation for any discrepancy will be inquired and provided in the eCRF.

Proprietary confidential information. © 2014 Boehringer Ingelheim International GmbH or one or more of its affiliated companies.

5. VARIABLES AND THEIR ASSESSMENT

5.1 EFFECTIVENESS

5.1.1 Endpoint(s) of effectiveness

The effectiveness endpoint is the incidence rate of stroke or systemic embolism (definitions are provided in Section 5.1.2.)

5.1.2 Assessment of effectiveness

Since the patient follow-up period is only 12 weeks (in case of long-term FU, 24 weeks), it is not possible to perform any meaningful effectiveness assessment of Pradaxa in this NIS. However, since it is a requirement to evaluate also effectiveness in all regulatory requisite NIS in Korea and as requested by **MFDS**, a descriptive analysis of effectiveness endpoint will be performed.

Effectiveness analysis will be performed to the patients who have been on Pradaxa more than 12 weeks (in case of long-term FU, 24 weeks).

The following definitions apply and should be used as a guide when reporting a thrombotic event:

Stroke:

Stroke is an acute onset of a focal neurological deficit of presumed vascular origin lasting for 24 hours or more or resulting in death. The stroke is categorized as ischemic or hemorrhagic or uncertain classification (based on CT or MR scanning or autopsy). Fatal stroke is defined as death from any cause within 30 days of stroke. Severity of stroke will be assessed by modified Rankin Scale (see Table 10.1:4) at discharge from hospital and/or at 3-6 months later (if available).

Systemic embolism:

Systemic embolism is an acute vascular occlusion of the extremities or any organ (kidneys, mesenteric arteries, spleen, retina or grafts), typically documented by angiography, surgery, scintigraphy, or autopsy.

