6.2.2.2 Visit 2 (12 \pm 2 weeks from Visit 1)

After 12 \pm 2 weeks from Visit 1, the patients will return for follow-up. The followings will be noted and recorded in the eCRF:

Proprietary confidential information. © 2014 Boehringer Ingelheim International GmbH or one or more of its affiliated companies.

- Visit date
- Any change of Pradaxa dose given
- Any changes in laboratory tests which required actions on drug dosage since last visit or any laboratory values performed to monitor the increased risk of bleeding ie. aPTT
- Vital signs: average blood pressure (sitting arm) and pulse rate
- Effectiveness endpoints: incidence of stroke or systemic embolism
- Anti-thrombotic therapy: any change in the anti-thrombotic therapies since last visit (excluding Pradaxa)
- Concomitant medications including new medications taken since last visit: any change in the concomitant medications (dose and dosing intervals)
- Any adverse events noted
- Treatment compliance
- **Study completion status: for the prematurely withdrawn patients, this section should be recorded to assess the safety information and the reason for withdrawal**
- NIS physician's electronic signature for data integrity (do not record this section for long-term FU cases)

At Visit 2, the patients on long-term follow-up will be reminded to contact the NIS physician in the event of any adverse events noted hereafter.

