7. STATISTICAL METHODS AND DETERMINATION OF SAMPLE SIZE

Details are provided in the statistical Trial Statistical Analysis Plan (TSAP).

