7.3 PLANNED ANALYSES

7.3.1 Primary analyses

A descriptive analysis of effectiveness endpoints is planned. For patients treated with Pradaxa incidence of stroke or systemic embolism will be calculated. Effectiveness analyses will be performed based on demographics and baseline characteristics. However, if data for patients who have been treated with Pradaxa beyond the scope of approved label are collected, separate effectiveness analyses will be conducted.

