7.3.3 Safety analyses

Demographic and baseline characteristics (including specifically stroke/bleeding risk scores (CHADS₂, CHA₂DS₂-VASc and HAS-BLED)) will be summarized descriptively for the entire cohort of eligible patients.

Adverse events (AEs) will be coded according to the latest version of Medical Dictionary for Drug Regulatory Affairs (MedDRA) coding system. Concomitant therapies will be coded according to the latest version of KIMS (Korea Index of Medical Specialties) coding system. The trial database will not be locked until coding is complete.

Safety analyses will be based on all patients treated, i.e. all patients who received at least one dose of Pradaxa. However, if data for patients who have been treated with Pradaxa beyond the scope of approved label are collected, separate safety analyses will be performed. Safety analyses will be performed based on demographics and baseline characteristics.

Proprietary confidential information. © 2014 Boehringer Ingelheim International GmbH or one or more of its affiliated companies.

Patients lost to follow up will be characterized compared to the remaining patients and reason and time point of loss to follow up will be evaluated.

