7.4 HANDLING OF MISSING DATA

As this is non-interventional study, there are no required investigations and diagnostic procedures (e.g. lab, ultrasound).

Maximum attempt will be made to ensure the completeness of data collection. All available data will be used in the data analysis. There will be no imputation of data to fill the missing values.

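### The effectiveness set requires more than 12 (or 24) weeks on Pradaxa, so a stroke that is fatal before the cut-off is never counted in the incidence

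*Combined protocol and SAP*

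**What the plan says.** Section 5.1.1 sets the endpoint: "The effectiveness endpoint is the incidence rate of stroke or systemic embolism". Section 5.1.2 restricts the patients analysed: "Effectiveness analysis will be performed to the patients who have been on Pradaxa more than 12 weeks (in case of long-term FU, 24 weeks"). Its stroke definition covers a deficit "lasting for 24 hours or more or resulting in death", and it goes on to define fatal stroke separately.

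Section 7.3.1 describes the population without a minimum duration: "For patients treated with Pradaxa incidence of stroke or systemic embolism will be calculated". Section 7.3.3 bases safety on "all patients who received at least one dose of Pradaxa". Follow-up in section 6.2.2 is 12 or 24 weeks with a window of 2 weeks either side, so the cut-off falls at the end of planned observation. Section 6.2.2.2 records the endpoint at Visit 2 for all patients, including long-term ones: "Effectiveness endpoints: incidence of stroke or systemic embolism".

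Section 7 defers further detail: "Details are provided in the statistical Trial Statistical Analysis Plan (TSAP"). That plan is not among the documents.

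**The concern.** Membership of the effectiveness set depends on something that happens after baseline and that the endpoint itself can determine. Death before week 12 (or 24) removes the patient, so a stroke fatal in that period has zero chance of being counted. A non-fatal stroke or embolism that leads to stopping Pradaxa early removes the patient as well. Read literally, a long-term patient who stops between weeks 12 and 24 also leaves the set, although the endpoint was recorded at Visit 2.

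At stake is the incidence figure that section 5.1.2 says the authority asks for. It would omit some of the most severe events. The effectiveness and safety tables could also show different stroke counts with nothing in the protocol to explain the difference.

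**Working it through.** There is no stated figure to reproduce: the sample size of 3,000 is a regulatory requirement, and no event rate is given. The defect follows from the definitions; the arithmetic only shows its possible size.

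**From the documents:** 1,500 patients planned for 12 weeks and 1,500 for 24 weeks (sections 6.2.2 and 7.6).

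**Assumed, because the documents do not give them:**
- q: share of event patients who fail the cut-off.
- d: share of all patients who fail it.
- f: fraction of planned time contributed by those who fail; 0.5 unless stated.
- c: share of event patients who die before the cut-off.

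**1. Incidence as a proportion.** Reported / all-treated = (1 − q)/(1 − d).

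| | d = 10% | d = 20% | d = 30% |
|---|---|---|---|
| q = 50% | 0.56 | 0.63 | 0.71 |
| q = 30% | 0.78 | 0.88 | 1.00 |

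There is no bias at q = d, and the ratio exceeds 1 if q < d.

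**2. Incidence per person-time.** Reported / all-treated = (1 − q)[(1 − d) + d·f]/(1 − d).

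| | d = 10% | d = 20% | d = 30% |
|---|---|---|---|
| q = 50% | 0.53 | 0.56 | 0.61 |
| q = 30% | 0.74 | 0.79 | 0.85 |

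The ratio equals 1 at q0 = d·f/[(1 − d) + d·f], which is 5.3%, 11.1% and 17.6% for d = 10, 20 and 30%. Above that the rate is biased downward. At d = 20%, q0 is 5.9% with f = 0.25 and 15.8% with f = 0.75.

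**3. Early fatal strokes alone.** Let the other event patients fail only at the neutral rate: q = c + (1 − c)d for the proportion, q = c + (1 − c)q0 for the rate. Both ratios then reduce to 1 − c, whatever d is: 0.90, 0.80 and 0.70 for c = 10, 20 and 30%.

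**4. In counts.**
- Planned follow-up is 1,500 × 12 + 1,500 × 24 = 54,000 patient-weeks; × 7/365.25 = 1,035 patient-years.
- With d = 20% and f = 0.5, all treated patients contribute 0.9 × 1,035 = 931 patient-years and the restricted set 0.8 × 1,035 = 828.
- At an assumed 2 events per 100 patient-years, the all-treated set yields 0.02 × 931 = 18.6 events.
- With c = 20%, q = 0.2 + 0.8 × 0.111 = 0.289, leaving 18.6 × 0.711 = 13.2 events.
- With q = 50%, 9.3 events remain.

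| Set | Events (rounded) | Per 100 patient-years | Exact Poisson 95% CI |
|---|---|---|---|
| All treated | 19 | 2.04 | 1.23 to 3.19 |
| Restricted, c = 20% | 13 | 1.57 | 0.84 to 2.69 |
| Restricted, q = 50% | 9 | 1.09 | 0.50 to 2.06 |

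**The case against.** The restriction stands in one sentence. The synopsis and sections 5.1.1 and 7.3.1 do not repeat it, and the analysis plan may define the set differently. That limits the point to the protocol wording. It does not remove it, because no section lifts the restriction or exempts patients who have an event.

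The magnitude is hypothetical. The proportion can be unbiased, or even too high, if event patients fail the cut-off no more often than others, so only the loss of early fatal strokes is certain in direction. The intervals above overlap heavily. Both remarks are correct; the case rests on systematic omission, not on a statistical contrast.

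The lower threshold for the rate depends on f. If everyone who fails the cut-off were followed for the full planned time (f = 1), the rate ratio would become (1 − q)/(1 − d) and the threshold would rise to d. Full follow-up cannot hold for patients who die, so the threshold stays below d, but its size is uncertain.

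Some supporting comparisons are weak. Different sets for safety and effectiveness are not an error in themselves. The statement in section 7.4, "All available data will be used in the data analysis", concerns missing values rather than the analysis set. The 24-week parenthesis might mean two separate analyses instead of excluding long-term patients who stop after week 12.

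Finally, effectiveness is secondary (section 2.2.2), no hypothesis is tested (section 7.2), and section 5.1.2 itself disclaims a meaningful assessment. Section 3.2 plans to obtain vital status where possible and to characterise patients lost to follow-up. An early fatal stroke would be visible in the safety tables. All this limits the consequence, but none of it puts the event back into the effectiveness incidence.

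**Conclusion.** The concern holds on the protocol wording and should be fixed. Strokes fatal before the cut-off are excluded with certainty. Other events that end treatment early are excluded too, and they bias the result downward only if event patients fail the cut-off more often than the neutral rate: d for a proportion, a lower value for a rate per person-time. Under the neutral assumption for the remaining event patients, early deaths alone scale the incidence by 1 − c. Every rate and share used here is assumed. The primary safety objective is unaffected, and nothing is concluded about the analysis finally performed.

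**What to change.** Reword sections 5.1.2 and 7.3.1 to the same effect, and align the trial statistical analysis plan:

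- The primary effectiveness set is every patient who took one or more doses of Pradaxa.
- The first stroke or systemic embolism after the first dose counts. Patients without an event are censored at last contact or death.
- Report events per 100 patient-years with a 95% confidence interval, overall and for the short- and long-term cohorts, with events on treatment and after stopping shown separately.
- Keep the set treated for more than 12 or 24 weeks only as a labelled supplementary analysis. State whether its cut-off means the nominal duration or completion within the visit window. The synopsis gives 12±2 and 24±2 weeks, so a literal reading may drop patients who completed on time.

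The cost is wording, some analysis work and possibly a less favourable incidence. No new visits are needed: section 5.2.2.2 already collects adverse events from the start of treatment to 7 days after the last follow-up visit, and sections 6.2.2.2 and 6.2.3 seek safety information on withdrawn patients. Capture after stopping may be incomplete, since section 6.2.3 obtains vital status only where possible. The report should state this as a limitation; it is one reason for the separate display.

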Duration of treatment:	1) Treatment duration for short-term surveillance: 12±2 weeks, long-term surveillance: 24±2 weeks 2) Study duration: 6 years (Study period required by the Ministry of Food and Drug Safety (MFDS) is from 18 Feb 2011 to 17 Feb 2017. Interim reports are expected biannually for the initial two years and annually thereafter by May 2017.)		
Criteria for effectiveness:	Incidence of stroke or systemic embolism		
Criteria for safety:	All reported adverse events in patients who have taken at least one dose of Pradaxa will be noted.		
Statistical methods:	Descriptive statistics		

Proprietary confidential information. © 2014 Boehringer Ingelheim International GmbH or one or more of its affiliated companies.

FLOW CHART

Data points	Baseline	Follow-up 1(Short-term)	Follow-up 2(Long-term)
Visit Number	1	2	3
Week/s	0	12±2	24±2
Diagnosis	X		
Inclusion / exclusion criteria	X		
Demographics	X		
Renal Function	X		
Lifestyle factors	X		
AF disease characteristics	X		
Medical history	X		
Anti-thrombotic therapy	X	X	X
Concomitant medications	X	X	X
Pradaxa administration status	X	X	X
Vital signs	X	X	X
Effectiveness endpoints		X	X
Changes in lab tests together with action on drugs		X	X
Adverse events		X	X
Treatment compliance		X	X
Study completion		X	X

Proprietary confidential information. © 2014 Boehringer Ingelheim International GmbH or one or more of its affiliated companies.

TABLE OF CONTENTS

TITLE PAGE	1
NON-INTERVENTIONAL STUDY PROTOCOL SYNOPSIS	2
FLOW CHART	5
TABLE OF CONTENTS	6
ABBREVIATIONS	9
1. INTRODUCTION.....	10
1.1 MEDICAL BACKGROUND.....	10
1.2 DRUG PROFILE	11
2. RATIONALE, OBJECTIVES, AND BENEFIT-RISK ASSESSMENT	12
2.1 RATIONALE FOR PERFORMING THE STUDY	12
2.2 STUDY OBJECTIVES.....	12
2.2.1 Primary objective	12
2.2.2 Secondary objective	12
2.3 BENEFIT-RISK ASSESSMENT	12
3. DESCRIPTION OF DESIGN AND STUDY POPULATION	13
3.1 OVERALL DESIGN AND PLAN	13
3.1.1 Administrative structure of the study	13
3.2 DISCUSSION OF STUDY DESIGN.....	13
3.3 SELECTION OF POPULATION	14
3.3.1 Main diagnosis for study entry	14
3.3.2 Inclusion criteria	14
3.3.3 Exclusion criteria	14
3.3.4 Removal of patients from therapy or assessments.....	15
3.3.4.1 Removal of individual patients (therapy or assessments)	15
3.3.4.2 Discontinuation of the study by the sponsor	15
4. TREATMENTS.....	16
4.1 PRESCRIBED TREATMENTS TO BE OBSERVED.....	16
4.1.1 Identity of the product(s).....	16
4.1.2 Method of assigning patients to treatment groups	16

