3.2 DISCUSSION OF STUDY DESIGN

This is a single arm study with dabigatran etexilate mesilate cohort.

Loss to follow up

All efforts will be made to minimize loss to follow up, particularly in the tracking of lost patients. To the extent possible, vital status, at minimum, for patients lost to follow up will be obtained. This allows assessing the impact of informative censoring due to treatment discontinuation. Also, patients lost to follow up will be characterized compared to the remaining patients and reason and time point of loss to follow up will be evaluated.

Channeling bias

Channeling bias can occur due to preferential prescribing in relation to different risks for the events of interest: e.g., if dabigatran would be more often prescribed to higher risk patients compared to other treatments, higher incidences of outcome events were then expected in the dabigatran group.

Information and recall bias

Information bias can e.g. occur due to selective reporting of already established and known adverse effects for a known product as compared to a new product (dabigatran), or vice versa. A standardized data collection form will be used for assessing exposure and AEs. These standardized procedures for data collection are intended to minimize such biases. Recall bias may be caused, e.g. if visits are separated by long time intervals and patient forget certain information. It can be reduced by associating questions with specified time intervals (e.g. how often did you take this co-medication *during the last 5 days*).

Proprietary confidential information. © 2014 Boehringer Ingelheim International GmbH or one or more of its affiliated companies.

Confounding

As in any observational study, confounding may affect the estimation of association between drug exposure and outcome of interest and statistical techniques. However, as only major confounders for selected research questions can be captured, residual (unmeasured) confounding may remain.

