5.2.2.2 Adverse event and serious adverse event reporting

All adverse events occurring from the start of Pradaxa treatment up to 7 days after last follow-up visit need to be collected, documented and reported to the sponsor using the AE reporting form of eCRF (Attachment 1). All SAEs must be reported with details of non-serious AEs occurring at the same time, within 24 hours of occurrence via telephone/fax to the Clinical Safety Officer (CSO) of BI Korea using the SAE report form (Attachment2). If any new or further information to these events is available, a follow-up SAE report has to be sent to BI. All SAEs and non-serious AEs must include a causal relationship assessment from the physician.

All other Adverse Events must be reported on the eCRFs within 2 weeks to the Sponsor.

Contact details:

Clinical Safety Officer

[contact]

[contact]

Address: Boehringer Ingelheim Korea, Medical Dept.

[name]

Pregnancy

Rarely, patients taking part in non interventional studies can get pregnant. Once a patient enrolled into the study and exposed to Pradaxa becomes pregnant, the NIS physician will stop the drug and report immediately to the sponsor. Drug exposure during pregnancy has to be reported immediately (within 24 hours or next business day, whichever is shorter) to CSO. Furthermore, the details of all the drugs to which the patient exposed at the time of pregnancy will be recorded. The outcome of the pregnancy associated with the drug exposure will be assessed. In the absence of an (S)AE, only the Pregnancy Monitoring Form (Attachment 3) for NIS, not the SAE form is to be completed. The ISF will contain the Pregnancy Monitoring Form (Part A and Part B) and those forms could be downloaded from eCRF website.

Proprietary confidential information. © 2014 Boehringer Ingelheim International GmbH or one or more of its affiliated companies.

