6.2.2 Treatment period(s)

As per regulations, enrolled patients will be followed up for a 12 week or 24 week treatment period. There will be a visit window of ± 2 weeks. To minimize the selection bias at the site level, the goal is to have participating centers reflect a balance between general hospitals and clinics for short-term or long-term surveillances.

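### The effectiveness set requires more than 12 (24) weeks on Pradaxa, so a stroke or embolism that ends treatment early removes the patient and biases the incidence downward

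*Combined protocol and SAP*

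**What the plan says.** Section 5.1.1 sets the endpoint: "The effectiveness endpoint is the incidence rate of stroke or systemic embolism". Section 5.1.2 then restricts who is analysed: "Effectiveness analysis will be performed to the patients who have been on Pradaxa more than 12 weeks (in case of long-term FU, 24 weeks"). The same section includes strokes that result in death and adds: "Fatal stroke is defined as death from any cause within 30 days of stroke".

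Other parts of the protocol bear on this:

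- Section 7.3.1 describes the calculation with no minimum duration: "For patients treated with Pradaxa incidence of stroke or systemic embolism will be calculated".
- Section 7.3.3 bases the safety analyses on everyone who took one dose or more.
- Section 3.2 plans to obtain vital status for patients lost to follow-up and explains: "This allows assessing the impact of informative censoring due to treatment discontinuation".
- The synopsis gives the observation periods: "Treatment duration for short-term surveillance: 12±2 weeks, long-term surveillance: 24±2 weeks". Section 6.2.2 repeats the tolerance: "There will be a visit window of ± 2 weeks".
- Section 7 refers to a separate TSAP for details. It is not among the documents.

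**The concern.** Membership of the effectiveness set is decided after baseline, by something the outcome itself can determine. A fatal stroke ends treatment, and a disabling or haemorrhagic stroke may lead the physician to stop it. Such patients leave both numerator and denominator. Because events are few relative to patients, the loss from the numerator dominates, so the error has a known direction: the incidence is too low.

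This incidence is the study's only effectiveness result, and section 5.1.2 says it is produced at the regulator's request. Under the rule, the report could list a stroke as a serious adverse event while the effectiveness table omits it. Section 5.1.2 does warn that effectiveness cannot be assessed meaningfully, but the reason it gives is short follow-up. It does not mention selection on survival or persistence, so a reader would not know to expect it.

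A second, smaller matter is that the threshold sits at the middle of the permitted visit window rather than at its start.

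**Working it through.** The plan states no event rate, stopping rate or precision for this endpoint, so there is no figure of its own to reproduce. The cohort sizes in section 7.6 are consistent: 1,500 + 1,500 = 3,000.

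**1. Fatal strokes that the rule always excludes.** Inputs: thresholds of 84 and 168 days and the 30-day definition (both section 5.1.2). Assumptions: dosing starts at Visit 1, and long-term patients face the 24-week cut only. With onset on day t, death occurs by day t + 30. The patient cannot exceed threshold T if t + 30 ≤ T.

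- Short-term: t ≤ 84 − 30 = 54, which is 54/84 = 64% of the days up to the threshold.
- Long-term: t ≤ 168 − 30 = 138, which is 138/168 = 82% of those days.

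These are shares of days, not of strokes. A later stroke is also lost if death follows fast enough.

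**2. Size of the bias as a function of the unknown share.** Let E be the events among N treated patients, and q the share of event patients who die or permanently stop before the threshold. The restricted set reports E(1 − q)/(N − Eq). Since E is small relative to N, the ratio to the true incidence is close to 1 − q. Stopping that is unrelated to events and removes both groups in proportion cancels out.

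Illustration at an assumed 2 events per 100 person-years and nominal follow-up:

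- Short-term: 1,500 × (1 − exp(−0.02 × 12/52)) = 6.91 events.
- Long-term: 1,500 × (1 − exp(−0.02 × 24/52)) = 13.78 events.
- Together: 20.7 events, or 20.7/3,000 = 0.69%.

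| Assumed q | Reported incidence | Ratio to true |
|---|---|---|
| 25% | 0.52% | 0.75 |
| 50% | 0.35% | 0.50 |
| 75% | 0.17% | 0.25 |

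At assumed rates of 1 to 3 per 100 person-years, the same formula gives about 10 to 31 events. With q = 50%, about 5 to 15 of them would drop out.

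**3. Would a lower threshold cure it?** Suppose a share p of event patients leave at the event, the hazard is low and constant, and the final visit is on day V. Then the ratio is 1 − p × T/V. Take p = 50% and, by assumption, final visits at week 13 (V = 91) or week 25 (V = 175).

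- Current thresholds: 1 − 0.5 × 84/91 = 0.54 and 1 − 0.5 × 168/175 = 0.52.
- Thresholds of 10 and 22 weeks: 1 − 0.5 × 70/91 = 0.62 and 1 − 0.5 × 154/175 = 0.56.

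Most of the bias remains.

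**4. Completers near the threshold.** On-schedule final visits fall on days 70–98 or 154–182, which is 29 days each. The days that fail the threshold depend on where exposure is taken to end:

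- At the final visit: days 70–84 or 154–168 fail, 15 of 29.
- Seven days after it, borrowing the adverse-event collection limit in section 5.2.2.2: days 70–77 or 154–161 fail, 8 of 29.
- If prescribing that continues after the visit is counted, or the ±2 weeks is read into the threshold: possibly none.

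The protocol does not say which applies.

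**The case against.** The best defence is that section 5.1.2 may not be the last word. Section 7.3.1 omits the restriction, section 7.4 says that all available data are used, the endpoint is recorded at each follow-up visit without a duration condition, and the TSAP may define the set differently. That stands as a reason for caution. But none of the available text withdraws the restriction, and two sections that differ still need to be reconciled.

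It is also fair that the consequences are limited. Effectiveness is the secondary objective, and all analyses are descriptive. Events remain in the primary safety data for everyone dosed: "All adverse events occurring from the start of Pradaxa treatment up to 7 days after last follow-up visit need to be collected". Vital status is sought for lost patients. A patient with a non-fatal event who stays on Pradaxa past the threshold is kept. All of this stands, but none of it corrects the effectiveness figure.

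Some stronger readings are tempting and are not supported:

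- A reader might infer that about half of all events will be lost. The documents give no share of event patients who die or stop, so the 50% case is only an illustration.
- A reader might infer that 64% and 82% of fatal strokes disappear. Those are shares of days. The day-138 figure also fails if long-term patients enter a 12-week tabulation as well, which the wording does not rule out.
- A reader might infer that over half of on-schedule completers are dropped. The 15 of 29 counts calendar days under one counting rule; no visit-date distribution is given.

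**Conclusion.** The concern holds for patients who die or permanently stop Pradaxa before the threshold because of a stroke or systemic embolism. On the wording of section 5.1.2 they are excluded, and the reported incidence is biased downward. The direction follows from the rule itself; the overall size does not follow from the documents and is governed by q. The day-54 and day-138 limits rest on dosing from Visit 1 and a literal threshold, with the strict 24-week cut for long-term patients.

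The mismatch with the visit window is a lack of clarity that might cost some completers, not an established loss. The point deserves correction because it affects the study's only effectiveness result. It does not touch the safety analysis or the sample size, and no hypothesis test depends on it.

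**What to change.** In section 5.1.2, replace the minimum-duration rule with the following:

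- **Set:** all patients who took at least one dose of Pradaxa, the same population as for safety.
- **Measure:** first stroke or systemic embolism per person-time, counted from first dose to the earliest of event, death, loss to follow-up or last follow-up visit.
- **On-treatment version:** the same rate, censored at a stated time after the last dose, for example 7 days.
- **Supplementary only:** the completers table, with a threshold of at least 10 or 22 weeks to match the window. As working step 3 shows, lowering the threshold is not a substitute for the change of set.

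Section 7.3.1 and the TSAP should then name the same set.

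The cost is a little more analysis work and a protocol amendment, which under section 8.1 goes through ethics and authority review. The eCRF must hold dose start and stop dates and event dates. Section 8.4.2 already asks for the onset date and the action taken with Pradaxa for each adverse event, but the eCRF is not among the documents, so this needs confirming.
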